5.1 Description

Cervical cerclage is a surgical procedure done under anesthesia. It consists of a suture/tape surgically placed around the cervix as close as possible to the high of the internal os. The surgery is performed through the vagina. This suture is a non-absorbable sterile material and needs to be removed later during pregnancy or before delivery.

5.2 Treatment Regimens

Subjects will be randomized in a 1:1 fashion to either receive the physical exam indicated cerclage, or expectant management. Women will still be able to withdrawal from the study after randomization if they feel that either expectant management or cerclage have an unacceptable risk of extreme premature delivery with increased risk of severely handicap children.

5.2.1 Physical exam indicated cerclage

For those randomized to physical exam indicated cerclage placement, the surgical procedure will be scheduled in the operating room under anesthesia prior to insurance precertification.

5.2.2 Expectant management

For those randomized to expectant management, they will continue routine pregnancy care.

5.3 Method for Assigning Subjects to Treatment Groups

A computer system will be used to communicate the randomization assignments to the trial staff. Subjects will be randomized centrally using blocks of randomly varying size (e.g, 2, 4 and 6).

5.4 Placement of Cerclage

Physical exam indicated cerclage is placed by trained physician in the operating room under anesthesia (regional or general at the discretion of the anesthesiologist). Antibiotics prior to the procedure and tocolysis with indomethacin, amniocentesis to rule out chorioamnionitis, amnioreduction, surgical technique, election of sutures, and admission to the hospital for observation or maternal physical activity after randomization will be at the discretion of the attending physician performing the cerclage.

6 Study Procedures

6.1 Cervical evaluation

Potential study subjects will be identified from 2 different sources:

- 1.1. Transvaginal ultrasound cervical length will be offered at the time of a routine second trimester fetal anatomy ultrasound exam between 16-23 6/7 weeks gestation as part of the PoPPTs study (IRB approved), verbal consent will be requested prior to transvaginal ultrasound.

1.2. Patients presenting at emergency room in labor and delivery (triage, TJU 7th floor) between 16-23 6/7 weeks gestation, which may require a pelvic evaluation as part of their triage assessment (verbal consent will be requested as per standard of care)

6.2 Randomization

Patients with dilated cervix and visible membranes who are eligible and consent to participate in the study will be randomly assigned to one of two groups: Physical exam indicated cerclage or standard expectant obstetric management. Subjects will be randomized using random block sizes of four. Patients allocated to the physical exam indicated cerclage group will have the cerclage surgically placed.

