3.1 General Design

This is a multi-center, open-label, randomized study. Women with twin gestations that have dilated cervix (1-5cm) with visible membranes during ultrasound, pelvic exam and/or speculum exam will be invited to participate in the trial.

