4. **Randomization:** If the patient agrees to participate in the study, the informed consent form will be signed and a copy will be given to the patient. Subjects with dilated cervix 1-5 cm and visible membranes who are eligible and consent to participate in the study will be randomly assigned to one of two groups: Cervical cerclage or standard obstetric management. Subjects will be randomized using blocks of randomly varying size (e.g., 2, 4 and 6).
5. **Insurance precertification:** for those patients assigned to cerclage, an insurance precertification process will be requested. If the patient doesn't have insurance, a medical necessity letter will be provided, coverage will be requested and financial office will be consulted. The patient will be notified of the precertification outcome. At this time, insurance companies are routinely covering the procedure and the costs associated with it.
6. **Cervical cerclage:** After insurance approval, cerclage will be scheduled in the operating room under anesthesia. Amniocentesis prior to the cerclage to rule out chorioamnionitis, surgical technique, type of suture, medications and maternal physical activity after surgery will be at the discretion of the surgeon.
7. After randomization, subjects will continue with their usual clinical prenatal visits, and will participate in the study until delivery. The study investigator will communicate with the subject's primary obstetrician and cerclage placement will be done by the study investigator. The primary obstetrician will be responsible for all prenatal care. Subjects will be given a phone number to call if they have any questions or concerns about the cerclage or the study. A physician who is knowledgeable about the study will be available at all times.
8. **Interim Contacts:** Subjects in both groups will be contacted by the research assistants monthly either by phone or in person at the time of their prenatal visit. The research assistants will ask the subjects if they have had any complications with their pregnancy including any evaluations and/or admissions for preterm labor, preterm contractions, vaginal discharge, vaginal bleeding or discomfort. (see appendix #1 and #2 for questionnaire)

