7.1 Sample Size Determination

Calculation of sample size was based on a reduction in the incidence of spontaneous delivery before 34 weeks from 80% in the expectant management group to 40% in the cerclage group, with a power of 80%. To detect this difference at a significance level of 5%, we will need to enroll a total of 46 subjects with 23 subjects in each arm, plus 10% for loss of follow up. Total 52 subjects with 26 subjects in each arm

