7.2 Statistical Methods

The primary outcome is spontaneous preterm birth before 34 weeks of gestation. Secondary outcomes include gestational age at delivery, interval between diagnosis and delivery, birth weight, spontaneous preterm birth rates at less than 24, 28, 32 and 37 weeks gestation, clinical chorioamnionitis and spontaneous rupture of membranes at less than 34 weeks gestation. Secondary safety outcomes include admission to NICU, neonatal death, length of stay in the NICU until discharge home, composite adverse neonatal outcome that includes necrotizing enterocolitis, intraventricular hemorrhage (grade 2 or higher), respiratory distress syndrome, retinopathy of prematurity and treatment for sepsis), and significant adverse maternal effects will include: intraoperative rupture of membranes, chorioamnionitis, postpartum hemorrhage (estimated blood loss and requirement of blood transfusion, cervical tear and uterine rupture).

Statistical analysis will be based on the intention-to-treat principle.

Comparisons between the two groups will be made with the Mann-Whitney U test. Univariate comparisons of dichotomous data will be performed with Fishers exact test. The p values for all hypotheses will be two sided, and p values of less than 0.05 will be considered to be significant. The risk of spontaneous preterm birth before 34 weeks will be quantified by use of the relative ratio and 95% CI. Multivariate analysis will be performed using logistic regression. The risk of spontaneous preterm birth from randomization until 34 weeks will be assessed with Kaplan-Meier analysis, in which gestational age

is the timescale, spontaneous delivery is the event, and elective deliveries are censored. SPSS software package (version 16.0) will be used for all statistical analyses.

8 Safety and Adverse Events

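### Section 6.2 reads as a fixed block of four while sections 4.3, 5.3 and 7 call for randomly varying blocks; in this open-label trial a known fixed block could make up to about one third of assignments certain in advance, on average.

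*Combined protocol and SAP*

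**What the plan says.** Four places in the combined protocol and SAP describe the randomisation blocks.

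- Section 6.2 (Randomization): "Subjects will be randomized using random block sizes of four".
- Section 5.3 (Method for Assigning Subjects to Treatment Groups): "Subjects will be randomized centrally using blocks of randomly varying size (e.g, 2, 4 and 6"). This section also says that a computer system passes the assignments to trial staff.
- Section 4.3 item 4: "Subjects will be randomized using blocks of randomly varying size (e.g., 2, 4 and 6").
- Section 7 item 3 repeats the rule of 4.3 and adds that the system is computer based.

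On the setting, section 3.1 says "This is a multi-center, open-label, randomized study", and section 5.2 says "Subjects will be randomized in a 1:1 fashion to either receive the physical exam indicated cerclage, or expectant management". Sections 4.3 item 7 and 6.3 have study investigators place the cerclages. The Study Summary names a single study centre, although it also calls the trial multi-center, and sections 4.3 and 8.1 refer to all sites. No section says whether the list is stratified by site, and none says that block sizes are withheld from the staff who enrol.

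**The concern.** A single size cannot vary at random, so the sentence in 6.2 cannot be squared with the other three. Someone setting up or auditing the system could follow either rule, and the protocol could not later be cited to show which one was used.

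The choice matters because treatment is not masked and investigators who place the cerclages learn who received one. Central allocation hides the list, but it does not stop someone from working out the end of a block from the assignments already made. Some eligibility criteria rest on judgment (being asymptomatic, suspicion of chorioamnionitis), and up to 24 hours of observation come before the research approach. A recruiter who was sure of the next arm would therefore have some room to approach, or not approach, a particular woman. With 26 women per arm, each woman is 1/26 = 3.8 percentage points of an arm's event rate, so a few steered enrolments could move the primary comparison.

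**Working it through.** **Inputs.** Allocation 1:1 (5.2). Block of four (6.2), or varying sizes with 2, 4 and 6 as examples (4.3, 5.3, 7). Total 52 subjects (7.1), which is 52/4 = 13 complete blocks of four. The documents give no figure for predictability, so there is none to reproduce. The only figure of theirs used here is the 52, and it does reproduce: 80% against 40%, two-sided 5%, power 80%, no continuity correction, gives 23 per arm, and 46/0.90 = 51.1, rounded up to 52. The sample size is not affected by this point.

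**Step 1: fixed block of four, size and all earlier assignments on the list known.** There are 6 equally likely 2:2 arrangements.
- First and second assignments: never certain.
- Third: certain when the first two match, which is 2 of 6 arrangements = 1/3.
- Fourth: always certain.
- Expected certain per block = 1/3 + 1 = 4/3. As a proportion, (4/3)/4 = 1/3.
- Over 13 blocks: 13 × 4/3 = 17.3 of 52. Each block yields one or two certain assignments, so the possible range is 13 (25%) to 26 (50%).

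**Step 2: best-guess success, fixed four.** By position: 1/2, 2/3, (1/3 × 1 + 2/3 × 1/2) = 2/3, and 1. The mean is (1/2 + 2/3 + 2/3 + 1)/4 = 17/24 = 70.8%.

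**Step 3: varying blocks.** Assume 2, 4 and 6 are equally likely, the recruiter knows that set and all earlier assignments, but not the size of the current block. Updating the probabilities of the possible block states after each of 52 assignments, over 20,000 simulated lists, gives:

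| Rule | Certain in advance | Best guess correct |
|---|---|---|
| Fixed 4 | 33.4% (exact 33.3%) | 70.8% |
| 2/4/6, current size concealed | 4.0% (about 2 of 52) | 70.0% |
| 4/6, current size concealed | 5.6% | 69.0% |

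The last row is there because the protocol gives its sizes only as examples.

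**Step 4: if the current size were known under 2/4/6.** Expected certain assignments are 1, 4/3 and 3/2 for blocks of 2, 4 and 6. Then (1 + 4/3 + 3/2)/(2 + 4 + 6) = 23/72 = 32%. Varying the size helps only while the current size is concealed.

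**Step 5: several sites (number assumed).**
- One shared central list of fixed fours, S equal sites, staff seeing only their own assignments but knowing the position in the block: certainty requires that both earlier same-arm assignments in the block were their own, with probability 1/S². The proportion is (4/3)/4 × 1/S² = 1/(3S²): 33% for S = 1, 8.3% for S = 2, 3.7% for S = 3.
- Separate fixed-four lists per site: incomplete blocks lower the one third only slightly, to about 32%, 30% and 27% for 2, 4 and 8 equal sites.

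**The case against.** The best case for leaving this alone is that 6.2 is garbled text rather than a rival design. Three places agree on varying sizes, and two of them (5.3 and section 7 item 3) are presented as the method of assignment. Nothing shows that 6.2 would govern the system. That stands as a reason to expect that varying blocks are intended. It does not remove the contradiction.

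Several stronger readings are tempting, and the documents do not support them.

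- A reader might infer that one third of assignments would be predictable whatever the set-up. The figure needs knowledge of the block size and of every earlier assignment on the list. The trial is described as multi-center with central randomisation, and with three equal sites on a shared list fixed fours already give about 4%.
- A reader might take the list to be unstratified. The documents are silent.
- A reader might think that section 4.3 item 11, which lets a woman who declined join later, makes steering easy. It applies to women who themselves declined and who remain eligible up to 23 6/7 weeks. Delay changes a woman's slot only if someone else is enrolled first. At 52 subjects over three years (156 weeks), enrolment averages one every three weeks, within an eligibility window of at most eight weeks. The route is possible but not easy.
- A reader might conclude that the primary comparison is biased. No effect on the outcome has been estimated, and varying blocks barely change guessing.
- A reader might think the calculation requires the example sizes to be struck from the protocol. It does not: the 4% already lets the recruiter know that the set is 2, 4 and 6.

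**Conclusion.** The contradiction is real and should be corrected. If 6.2 were followed, and a recruiter knew the block size and saw the whole list (one centre, or site-specific lists), about one third of assignments on average would be certain in advance, against about 4% under 2/4/6. The 4% rests on equally likely sizes and a concealed current size. The benefit of varying blocks is the loss of certainty; best-guess success stays near 70%. On a list shared between sites that see only their own assignments, the exposure under fixed fours falls to about 8% for two equal sites and 4% for three, and the documents do not give the number of sites. What is shown is an opportunity for selection bias that costs almost nothing to close, not evidence that bias has occurred or will occur.

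**What to change.** Replace the block-size sentence in 6.2 with a reference to 5.3, so that 4.3, 5.3, 6.2 and 7 carry one rule: central computer randomisation in permuted blocks whose size varies at random, with the actual sizes not disclosed to enrolling staff. State in 5.3 whether the list is stratified by site, since that decides how much any one site can deduce. Confirm that the randomisation system is set to the rule in 5.3. Taking the example sizes out of the text is optional good practice.

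The cost is one wording amendment and, at most, one system setting. No additional subjects or staff are needed.

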6.3 Interim Contacts

Patients in both groups will be contacted by the research assistants monthly either by phone or in person at the time of their prenatal visit. The research assistants will ask the patients if they have had any complications with their pregnancy including any evaluations and/or admissions for preterm labor, vaginal bleeding, leaking of amniotic fluid, vaginal discharge and/or discomfort or if they received medications like antenatal steroids for fetal lung maturity, tocolysis or magnesium sulfate infusion. Consents for release of medical information will be signed at the time of randomization to gather medical information pertinent to the study in case of admissions to other institutions.

Patients will be instructed to report any adverse symptoms including pain, vaginal bleeding, contractions, decreased fetal movements and leakage of fluid immediately. They will be given a phone number to call if they have any questions or concerns about the study. A physician who is knowledgeable about the study will be available at all times. The study investigator will communicate with the patient's primary obstetrician; physical exam indicated cerclage placement will be done by one of the study investigators, but removal at any time can be done by the primary obstetrician. The primary obstetrician will be responsible for all prenatal care and delivery.

6.4 Cerclage Removal

1. The cerclage will be removed by the primary obstetrician during the 36th week of gestation. Removal of cerclage can be performed in the office or triage room, there is no need of anesthesia or admission to the hospital. Some reasons for early removal may include: active vaginal bleeding, preterm labor with persistent contractions despite tocolysis, cervical dilatation, prolapsed amniotic membranes through the cerclage, severe subject discomfort or subject request. Cervical cerclage removal involves: 1) sterile speculum exam, 2) identification of the knot of the suture or tape at the anterior lip of the cervix, 3) gentle traction of the suture and cut with scissors one side of the tape and pulling the tape out of the cervix, 4) expected discomfort associated with the speculum exam, pressure when pulling the suture/tape and minimal bleeding (one tablespoon).

6.5 Pregnancy Outcome

After subjects have delivered, information regarding outcome of the pregnancy and neonatal outcome until mother and neonate are discharge home. The information will be abstracted from the subjects'

medical records. A release of medical records consent will be signed at the time of randomization, in case the patient delivers at an outside institution.

7 Statistical Plan

1. This is a multi-center, open-label, randomized study
2. Subjects will be randomized in a 1:1 fashion to either receive the cervical cerclage, or standard obstetric management
3. Method for assigning subjects to treatment groups: A computer-based system will be used for the randomization assignments. Subjects will be randomized using blocks of randomly varying size (e.g., 2, 4 and 6).

7.1 Sample Size Determination

Calculation of sample size was based on a reduction in the incidence of spontaneous delivery before 34 weeks from 80% in the expectant management group to 40% in the cerclage group, with a power of 80%. To detect this difference at a significance level of 5%, we will need to enroll a total of 46 subjects with 23 subjects in each arm, plus 10% for loss of follow up. Total 52 subjects with 26 subjects in each arm

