1.2 Clinical Data to Date

A retrospective review of 12 women with twin pregnancies who underwent a physical exam-indicated cerclage (dilated cervix on examination or membranes visible at the external cervical os on speculum examination) during the second trimester were compared with 31 singleton pregnancies undergoing the same procedure from 1997 to 2012.²⁵ Comparing twins to singletons, the median time from cerclage placement to delivery was similar (92 vs. 106 days, p=0.3), as was the median GA at delivery (33.5 vs. 35.0 weeks, p=0.2). The likelihood of delivery at >32 weeks (75.0% vs. 71.0%, p>0.9) and the likelihood of neonatal survival to discharge (83.3% vs. 83.9%, p>0.9) were also similar. A case report of 4 women with twin pregnancy and cervical dilation with bulging membranes gave birth on an average of 48.5 days after cerclage placement.²⁶ A more recent publication evaluated 104 women with twin pregnancy vs. 334 singleton pregnancies with dilated cervix, median gestation at delivery was (31.9 weeks vs. 32.7 weeks) and delivery before 28 weeks (33.7% vs. 35.8%, P = .69) respectively.²⁸ **None of these publications have had an appropriate control group: twin gestation with expectant management.** Only one small retrospective cohort study had a control group with expectant management,²⁷ 23 women were identified with twin pregnancy, cervical dilation and visible membranes between 16-24 weeks; 16 underwent physical exam indicated cerclage while 7 received expectant management (control). In the control group 50% of the women were delivered prior to 24 weeks. Interval from time at diagnosis to delivery was significantly prolonged by approximately 6.8 weeks in the cerclage group, they had significant decreased SPTB ≤28 weeks (31.2% vs. 85.7% p=0.02) and increased neonatal survival upon discharge 71.8% vs. 42% (p=0.1).

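### The 80% power in 7.1 is about 73% at 46 evaluable women under the Fisher test named in 7.2, and neither planning rate has a stated source

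*Combined protocol and SAP*

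**What the plan says.** Section 7.1 plans for spontaneous delivery before 34 weeks to fall "from 80% in the expectant management group to 40% in the cerclage group, with a power of 80" per cent. It continues "To detect this difference at a significance level of 5" per cent and arrives at 46 women, 23 per arm, raised by 10% for loss to 52, or 26 per arm. It names neither the formula nor the test behind the calculation, and gives no source for the 80% or the 40%.

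Section 7.2 assigns Fisher's exact test to dichotomous comparisons and adds "The p values for all hypotheses will be two sided", with 0.05 as the threshold. The list that opens Section 7 sets 1:1 allocation: "Subjects will be randomized in a 1:1 fashion to either receive the cervical cerclage, or standard obstetric management".

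Three reports in Section 1.2 bear on the planning rates:

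- A series of 12 twin pregnancies with cerclage, compared with singletons: "the median GA at delivery (33.5 vs. 35.0 weeks, p=0.2").
- A series of 104 twin pregnancies, again compared with singletons: "median gestation at delivery was (31.9 weeks vs. 32.7 weeks").
- The only twin cohort with an expectant-management group (16 cerclage, 7 expectant): "they had significant decreased SPTB ≤28 weeks (31.2% vs. 85.7% p=0.02").

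**The concern.** Two things stand out. First, 23 per arm is a small number for an exact test. Fisher's test is conservative at this size, so a sample size taken from a normal approximation will not usually deliver its nominal power when Fisher is the analysis. Second, both twin series with a stated median have that median below 34 weeks, so at least half of those women had delivered by the endpoint's cut-off. That sits uneasily with a planned 40%.

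What is at stake is how a non-significant result is read. A trial described as 80% powered invites the conclusion that cerclage does not work. If the real chance of detecting the target effect is nearer 73%, or lower should the cerclage rate be above 40% with control at 80%, that conclusion is weaker than the protocol suggests.

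**Working it through.** **Inputs.** Control 80%, cerclage 40%, power 80%, alpha 5%, 23 and 26 per arm, 10% loss (7.1); two-sided testing and Fisher's exact test (7.2); 1:1 allocation (Section 7).

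**Step 1: reproduce 7.1.** Pooled normal approximation, no continuity correction, mean rate (0.8 + 0.4)/2 = 0.6:

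n = [1.960 × √(2 × 0.6 × 0.4) + 0.842 × √(0.8 × 0.2 + 0.4 × 0.6)]² / 0.4²
= [1.358 + 0.532]² / 0.16 = 22.3, so 23 per arm.

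Power at 23 per arm = Φ[(0.4 × √23 − 1.358) / 0.632] = Φ(0.886) = 81%. Allowing for loss, 23/0.9 = 25.6, so 26 per arm and 52 in all. The plan's figures reproduce. With a continuity correction the same formula gives 28 per arm, a first sign that 23 is too few for an exact test.

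**Step 2: power under the planned test.** For n per arm, sum Bin(i; n, control rate) × Bin(j; n, cerclage rate) over every pair (i, j) whose two-sided Fisher p value is below 0.05. At 80% vs 40% this gives 72.7% at 23 per arm and 79.9% at 26 per arm. The first size to reach 80% is 27 evaluable per arm. With the planned 10% loss, 26 × 0.9 = 23.4, so 23 per arm is the relevant row and 26 is the no-loss case.

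**Step 3: sensitivity to the rates.** Fisher power, 23 / 26 per arm:

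| Control | Cerclage 40% | Cerclage 45% | Cerclage 50% |
|---|---|---|---|
| 80% | 72.7% / 79.9% | 59.8% / 68.1% | 46.2% / 53.7% |
| 85.7% | 86.8% / 91.8% | 77.8% / 84.1% | 66.4% / 72.8% |
| 90% | 94.3% / 96.8% | 89.1% / 92.7% | 81.1% / 85.5% |

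To separate the effect of the rates from that of the test: at 80% vs 50% the normal approximation gives 57% / 63%. So at 23 per arm the change of rate alone takes power from 81% to 57%, and the change of test takes it on to 46%.

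**Step 4: smallest effect with 80% power.** Highest cerclage rate that still gives at least 80% Fisher power, from the same enumeration on a half-point grid:

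| Control | 23 per arm | 26 per arm |
|---|---|---|
| 80% | 36.5% (43.5 points) | 39.5% (40.5 points) |
| 85.7% | 43.5% (42.2 points) | 47.0% (38.7 points) |
| 90% | 50.5% (39.5 points) | 52.5% (37.5 points) |

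**Step 5: what 1.2 can say about the rates.**

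- *Cerclage, any cause.* Medians of 33.5 and 31.9 weeks mean at least 50% delivered before 34 weeks. If exactly 50% did, a 40% spontaneous rate needs 40/50 = 80% of those deliveries to be spontaneous, that is, one in five not. If 60% did, it needs 40/60 = 67%. The documents give no such split. At the 50% floor, exact 95% intervals are 21% to 79% (6/12) and 40% to 60% (52/104).
- *Cerclage, spontaneous.* The controlled cohort has 31.2% (5/16) by 28 weeks, exact 95% interval 11% to 59%. A 40% rate at 34 weeks leaves 40 − 31.2 = 8.8 points, or 0.088 × 16 = 1.4 women, for the next six weeks.
- *Control, spontaneous.* The same cohort has 85.7% (6/7) by 28 weeks, exact 95% interval 42% to 99.6%. The 34-week rate in that cohort cannot be lower.

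**The case against.** The strongest defence is that 7.1 contains no arithmetic error: 23 per arm is what a standard formula gives, and a target effect is a design judgement that need not equal a historical estimate. That stands. The difficulty is only that the formula does not match the test in 7.2. It is also fair that 7.2 asks for a relative risk with a 95% confidence interval, so imprecision in a null result would be visible. That softens the consequence but does not correct the stated power.

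Two stronger readings are tempting, and the documents support neither.

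- A reader might infer that the medians below 34 weeks make 40% impossible. They do not. The medians count deliveries of any cause, while the endpoint counts spontaneous delivery only. The series are small and have no expectant-management arm, and no passage reports spontaneous delivery before 34 weeks in either arm.
- A reader might infer that the cited data, taken together, show power below 80%. They fix no direction. The 85.7% is a 28-week figure from 7 women and so a floor for 34 weeks in that cohort. Pairing it with 50% gives 66% / 73%, but 90% vs 50% gives 81.1% / 85.5%. Even 85.7% vs 50% reaches about 81% at 26 per arm by the normal approximation.

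**Conclusion.** The point holds as a mismatch between stated power and planned test, together with unsourced planning rates. On the protocol's own rates, the 46 evaluable women give about 73% power under two-sided Fisher, a 27% chance of missing the target effect instead of 20%. The stated 80% is reached, to rounding, only if none of the planned 10% loss occurs. The 40% cerclage rate looks optimistic against 1.2 but is not excluded by it, and a control rate above 80% would offset some or all of the loss.

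This rests on three assumptions: that the Fisher test in 7.2 is the primary comparison, since it is the only test named there for two proportions; that rates other than 80% and 40% are scenarios, because the documents give no spontaneous rates before 34 weeks; and that the 104-woman series is a cerclage series, as its context and its title in the reference list indicate.

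**What to change.** Keep 52 women and revise the wording of 7.1:

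1. Name the calculation method, and state power for the two-sided Fisher test at 80% vs 40%: about 73% at 23 per arm and about 80% at 26 per arm.
2. Give the basis for both planning rates as rates of spontaneous delivery before 34 weeks, or say that they are assumptions.
3. Add the table from Step 3, covering cerclage 40% to 50% and control 80% to 90%.
4. Name the smallest effect detectable with 80% power. With control at 80%, that is a cerclage rate of about 36.5% at 23 per arm or about 40% at 26 per arm.

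The text should not say that 40% lies below what the cited series allow. The cost is a paragraph, a small table and a less favourable stated power. No additional women are needed, and neither the test nor any procedure changes.

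### The 80% power stated for 23 women per arm is not reached under the plan's own two-sided Fisher's exact test: it is 72.7% at 23/23 and at most 79.1% at any feasible split of 46

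*Combined protocol and SAP*

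**What the plan says.** Section 7.1 (Sample Size Determination) assumes that spontaneous delivery before 34 weeks falls "from 80% in the expectant management group to 40% in the cerclage group", with 80% power and a 5% significance level. It concludes that "we will need to enroll a total of 46 subjects with 23 subjects in each arm", then adds 10% for loss to follow-up, giving 52 women, 26 per arm. The section names neither the test nor the formula, and does not say whether the calculation is one- or two-sided.

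Section 7.2 (Statistical Methods) makes spontaneous preterm birth before 34 weeks the primary outcome and sets the tests: "Univariate comparisons of dichotomous data will be performed with Fishers exact test". On the threshold it says: "The p values for all hypotheses will be two sided, and p values of less than 0.05 will be considered to be significant". It also says: "SPSS software package (version 16.0) will be used for all statistical analyses".

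**The concern.** The power in 7.1 should describe the test that will decide the primary comparison. That outcome is dichotomous, and Fisher's test is the only test that 7.2 names for comparing dichotomous data between groups. Fisher's test is conservative in samples of this size, so a sample just large enough for an uncorrected chi-square test will usually be too small for it.

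At stake is the type II error. The plan accepts a 20% chance of missing a drop from 80% to 40%. If the true chance is higher, a non-significant result would be read as stronger evidence against cerclage than the design supports. The validity of a significant result is not in question.

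**Working it through.** **Inputs.** Event rates 80% (expectant) and 40% (cerclage), power 80%, level 5%, 23 evaluable and 26 enrolled per arm, all from 7.1. Two-sided p < 0.05 and Fisher's exact test, from 7.2. Allocation 1:1, from Section 7.

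**Step 1: reproduce the plan's figure.** The mean rate is 0.6 and the difference 0.4. The pooled two-sided formula without continuity correction gives

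n = [1.96·√(2·0.6·0.4) + 0.8416·√(0.8·0.2 + 0.4·0.6)]² / 0.4²
= [1.358 + 0.532]² / 0.16 = 22.33, so 23 per arm.

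Then 46/0.9 = 51.1, so 52. The plan's figures therefore reproduce, and the normal-approximation power at 23 per arm is 81.2%. That 7.1 used this formula is an inference. A one-sided continuity-corrected formula gives 22.2, so also 23, but 7.2 requires two-sided p values. The two-sided continuity-corrected formula gives 27.1, so 28.

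**Step 2: exact power under the test in 7.2.** For n₁ expectant and n₂ cerclage women,

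power = Σₐ Σ_b Bin(a; n₁, 0.8) · Bin(b; n₂, 0.4) · I[two-sided Fisher p(a, b) < 0.05],

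summed over every possible table. With 26 enrolled per arm, 46 evaluable women can split in seven ways:

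| Expectant/cerclage | Fisher power |
|---|---|
| 20/26 | 76.4% |
| 21/25 | 76.6% |
| 22/24 | 79.1% |
| 23/23 | 72.7% |
| 24/22 | 75.0% |
| 25/21 | 76.2% |
| 26/20 | 76.1% |

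All seven are below 80%. At 23/23 the type II error is 100 − 72.7 = 27.3%, against the stated 20%. For comparison, the uncorrected chi-square test has exact power 81.9% at 23/23, so the choice of test accounts for the shortfall.

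**Step 3: larger evaluable samples.** Fisher power is 79.9% at 26/26. The first equal split to reach 80% is 27/27 (80.2%). Power does not rise smoothly with sample size because the test is discrete: 25/24 gives 82.5% and 26/25 gives 83.1%, both above 26/26.

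**Step 4: average over losses.** The plan gives only the 10%. Assume that each of the 26 women per arm is lost independently with the same probability, and weight the power at each split by its binomial probability:

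| Scenario | Mean Fisher power |
|---|---|
| Exactly 46 evaluable | 75.5% |
| 10% loss | 77.3% |
| 5% loss | 80.3% |
| No loss (26/26) | 79.9% |

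**Step 5: an exact test with less conservatism.** Boschloo's unconditional test at the same two-sided 5% level has power 80.9% at 23/23 (maximum type I error 0.0475) and 85.1% at 26/26 (0.0484). Its mean power is 80.8% with 10% loss, 80.0% given exactly 46 evaluable, and 83.0% with 5% loss. The maximum type I error of Fisher's test at 23/23 is only 0.026, which is where its power is lost.

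**The case against.** The strongest reply has four parts.

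- **Nothing is miscalculated, and 23/23 is an unlucky point.** Both are true. Section 7.1 is correct for the formula it appears to use, so the fault is an inconsistency between 7.1 and 7.2. The 23/23 split is a trough caused by discreteness, and moving one woman to 22/24 gives 79.1%. Under independent 10% loss, exactly 23/23 occurs with probability 5.3% and exactly 46 evaluable with probability 16%. The 77.3% average, 2.7 points short, is thus the fairer summary of what to expect. But 23 per arm is the size to which 7.1 attaches its power, and no feasible split of 46 reaches 80%.
- **The trial enrols 52, and losses may be few.** The outcome is known at delivery and taken from medical records, with a signed release for delivery elsewhere. If losses are small, the gap nearly closes. However, the plan adds the six extra women for loss, and Section 5.2 allows withdrawal after randomization. Counting those women towards power assumes that the planned loss does not happen.
- **The assumed rates are more uncertain than the gap is wide.** This is fair. With a control rate of 82% instead of 80%, Fisher power is 78.1% at 23/23 and 84.8% at 26/26; a lower rate moves it the other way. But a power statement is conditional on its assumed rates, and it should be right for those rates.
- **Section 7.2 does not expressly tie Fisher's test to the primary outcome.** It does so only through the general rule for dichotomous data. The other analyses offer no competing group test: the relative ratio is an estimate, the logistic regression is labelled multivariate, and the Kaplan-Meier analysis names no test.

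**Conclusion.** The concern holds. At the planned rates and under two-sided Fisher's exact test, the stated 80% power is 72.7% at 23/23 and no more than 79.1% at any split of 46 available from 26 per arm. Averaged over independent losses it is 77.3% at the plan's 10% loss. It is essentially on target if 5% or fewer are lost.

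The enumeration needs only the plan's rates, level and test. The averages rest also on independent losses at the same rate in both arms. The conclusion depends on reading the rule for dichotomous data as covering the primary outcome, which is the natural reading. The error is a misstated power; it does not bias the comparison or inflate type I error. It should be corrected because it concerns the primary endpoint and is cheap to put right.

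**What to change.** In 7.1, name the test behind the calculation and make it agree with 7.2. There are two ways to do this.

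1. **Keep Fisher's test and restate the power.** For example: *With two-sided Fisher's exact test, power is about 73% with exactly 23 evaluable women per arm, about 75% on average with 46 evaluable, and just under 80% with all 52.* The assumption behind the average (independent, equal losses) should be stated with it. The cost is one sentence and a less favourable figure.
2. **Change the primary test.** Before any outcome data are seen, name Boschloo's unconditional exact test in 7.2 for spontaneous preterm birth before 34 weeks. The existing sample size then supports the 80% statement at 23/23 and on average over losses of up to 10%. The cost is an amendment to 7.2. If SPSS 16.0 does not provide the test, the software sentence must change too.

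Neither option requires more patients or alters trial conduct.
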